## **Experimental design**

Initially, an interview will be carried out via telephone (or in person for volunteers who do not have access to this means of communication), in which clarifications about the study will be carried out, as well as scheduling of the first visit. The first face-to-face visit will take place at the University, in which the participants will be introduced to the responsible research subjects, will receive the informed consent form and, if they agree with all the study procedures, will be invited to sign the term in two copies. In case of acceptance, the tests referring to the inclusion criteria will be applied (Baecke's Physical Activity Questionnaire, Mini Mental State Examination and Geriatric Depression Scale), as well the socioeconomic and quality of life questionnaires. If the volunteers reach the required score, respectively below 9.11 and above 24, the second visit will be scheduled. On the second visit, blood collection will be performed to assess the lipid profile.

Afterwards, the subjects will be scheduled for the third visit, in which the quadriceps muscle thickness and quality assessment, anthropometric assessments, as well as familiarization with the lower limb strength test will be performed. Physical tests will be performed on the fourth visit. After the evaluations, the participants will be randomly allocated to one of the two interventions or the control group. After 8 weeks,

a fifth visit will be held, where the physical tests will be reassessed, as well as the application of the questionnaire on affectivity with the intervention. At the end of the 12 weeks of training, participants will be reassessed on all tests.

## **Arms and Interventions**

*Traditional concurrent training:* The subjects will perform two sessions per week of traditional concurrent training, consisting of strength training followed by aerobic exercise over 12 weeks, with progressive intensities and training volumes. Each traditional concurrent training session will consist of specific warm-up performed on equipment for upper and lower limbs with a load of less than 30% of the training load. Then the bench press, low row, leg press, extension and knee flexion exercises will be performed. Participants will be instructed to perform the concentric phase of the movement in one second and the eccentric phase in two seconds. After strength training, aerobic training (walking outdoors or on a treadmill) will be performed with intensity based on the adapted BORG effort perception scale (ranged to 0 = minimum effort, to 10 = maximal effort).

*Concurrent training consisting of strength training combined with dance classes:* Each concurrent training session associated with dance classes will consist of the same strength training as the traditional concurrent training group, but the traditional aerobic training will be replaced by a dance class. Each dance class will consist of a 5-minute general warm-up with joint mobility exercises and dynamic stretching. Then the main part will be performed with the elaboration of choreography, lasting approximately 20 minutes. Finally, there will be a 5-minute cool-down with stretching exercises. Classes will be held in four different dance modalities, divided into four modules.

*Control group:* Subjects will be instructed to maintain their usual routine during the study period. After the end of the 12 weeks, the participants in the control group will be able to participate in one of the exercise groups according to their preference. The Control Group is necessary in this study, since some of the variables analyzed still have little evidence of the effects of physical exercise. For this reason, in addition to comparing protocols, it is also interesting to compare the results with a group that will not perform physical exercise.

## OUTCOME MEASURES

*Cognitive performance:* will be assessed through the Mini Mental State Examination (MMSE) which will be carried out following the recommendations of Lourenço & Veras (2006). The MMSE consists of answering a questionnaire with 11 open questions grouped into six categories: temporal and spatial orientation, processing, attention, calculation, evocation, language and constructive ability. The participant will be instructed to answer the 11 questions without asking for help.

*Physical activity level:* will be assessed using the questionnaire proposed by Simões (2009) which refers to the last 12 months of the elderly person's life and is divided into 3 domains. The first domain refers to daily life, the second to sports activities and the third to free time activities. The first domain will be evaluated according to frequency: 0= never, 1= sometimes, 2= almost always, 3= always, in this domain the sum of the answers is divided by the number of questions (10). Domains 2 and 3 will be evaluated according to codes: for intensity, weekly and annual duration. The product of the item codes for each activity is added across all activities, the sum of the different domains classifies individuals according to the level of physical activity: sedentary (< 9); active ( $\geq 9 \leq 16$ ); and athletes ( $\geq 17$ ) (SIMÕES, 2009). The cutoff point will be adopted in which individuals who reach a score  $\leq 9.11$  have a low level of physical activity; between 9.12 and 16.17 will be moderately active and  $\geq 16.18$  will be considered very active.

*Depressive symptoms:* will be measured using the Geriatric Depression Scale, that consists of 15 questions with binary answers (yes/no) and easy to understand. It ranges from zero (absence of depressive symptoms) to fifteen points (maximum score of depressive symptoms).

*Socioeconomic Characterization:* For sample characterization data, the elderly must answer the questionnaire from the Brazilian Association of Research Companies (ABEP, 2022) (Annex 6), which contains 15 socioeconomic indicators. The sum of answers generates a classification for the Brazilian population in strata from 0 to 100, being classes A, B1, B2, C1, C2, D and E).

*Quality of life:* will be assessed using the WHOQOL Questionnaire - ABRIDGED Version in Portuguese, following WHO recommendations (2011), which

consists of answering a questionnaire with 26 questions about your perception of quality of life. The participant will be guided to answer the questions with reference to the last two weeks. To complete the questionnaire, the individual will be instructed to circle the number that best represents their answer to each question, with 1 being the most negative answer and 5 being the most positive.

*Anthropometric measurements:* Body mass and height will be measured using a stadiometer and scale (0.1 kg resolution) (Urano, Canoas, Brazil). Waist circumference will be measured using a measuring tape (1 mm resolution).

*Dynamic balance:* will be measured using the Timed Up & Go test, according to the instructions by Podsiadlo & Richardson (1991), which consists of getting up from a standard chair (approximate seat height of 43 cm), walking a distance of 3 meters, go around a cone, walk back to the chair and sit down again.

*Static balance:* will be evaluated through the Single-Leg Stance Test performed according to the indications of Michikawa et al., (2009), which consists of remaining standing, with unipodal support as long as possible (with a limit of 60 seconds). The participant will be instructed to perform the test with the preferred leg.

*Ability to sit and stand:* will be evaluated through the 30s chair-stand test performed according to the indications of Rikli & Jones (1999), which consists of standing up and sitting on a chair as many times as possible during 30 seconds.

*Ability to climb stairs:* will be assessed using the Stair Climbing test performed according to the guidelines by Müller et al., (2021), which consists of climbing a ladder with 10 steps (approximate step height of 16 cm).

*Muscle thickness:* will be assessed by ultrasonography (Nemio XG, Toshiba, Japan) of the quadriceps. A transducer will be placed on the skin of the thigh of the individual's right leg, perpendicular to the tissue interface, after mapping the measurement site. The measurements will be performed with the participants lying down, after 10 minutes of rest and after 48 hours without vigorous physical activity. A water-based gel will be used to promote acoustic contact between the skin and the transducer. Three images of the rectus femoris, vastus medialis, vastus intermedius and vastus lateralis will be digitized and analyzed using Image-J software (National Institute of Health, USA). Measurements of the rectus femoris and vastus intermedius

will be taken at the midpoint between the greater trochanter and the lateral epicondyle of the femur, while the vastus lateralis will be at 30% of the distance from the lateral epicondyle of the femur to the greater trochanter. The subcutaneous adipose tissue-muscle interface and the muscle-bone interface will be identified, with the distance from the adipose tissue-muscle interface defined as muscle thickness. The thickness of the quadriceps femoris muscle of each leg will be considered as the sum of the four muscles mentioned.

*Specific tension (TE):* will be expressed as force per unit of muscle thickness and will be calculated by dividing the value of 1RM of knee extension by muscle thickness. Therefore, TE will be evaluated according to the following equation: [TE = 1RM (kg) of knee extension / muscle thickness (mm)]

*Lower limb strength:* will be evaluated through the 1RM test for the knee extension exercise, following the recommendations of Cadore et al., (2013), which consists of performing the knee extension exercise with the highest possible load for one repetition complete.

*Handgrip strength:* will be assessed through the handgrip strength test in a Palmar Dynamometer (Jamar Hydraulic Hand Dynamometer), following the recommendations of the American Society of Hand Therapists (MACDERMID et al., 2015), which consists of squeezing the handle of the dynamometer as hard as possible for 3 seconds.

*Cardiorespiratory capacity:* will be evaluated through the 6-minute walk test according to the indications of Rikli & Jones (1999), which consists of walking the maximum possible distance in six minutes.

*Affectivity through the intervention:* will be measured through the Affective Valence Scale, proposed by Rejeski et al., (1987), which consists of answering a quantified scale from +5 to -5. The participant will be instructed to respond to the scale with reference to their feelings throughout the training session and dance class. The scale has values from +5 to -5 that correspond, respectively, to the feelings "very good" and "very bad".

*Lower limb power output:* will be evaluated in the knee extension exercise at 30 and 70% of 1 RM. For this, the individuals will perform 5 repetitions at the

maximum possible speed in the concentric phase at each intensity (30 and 70%) of the exercise. The interval between each execution will be 2 minutes. The maximum and average power values will be determined through a linear displacement sensor (ChronoJump, Barcelona, Spain), coupled to the equipment.

Lipid profile: plasma concentrations of total cholesterol, HDL and triglycerides will be determined by the colorimetric method with specific kits in an automatic analyzer (Cobas C111, Roche Diagnostics, Basel, Switzerland). In addition, LDL lipoprotein levels will be estimated using the Friedewald equation (1972).

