## **Eligibility criteria**

Inclusion criteria: Be male or female aged between 65 and 75 years old; Do not practice regular physical exercises for at least three months; No history of competitive sports throughout life; Not having musculoskeletal and neurological diseases or disorders that may influence the performance of the exercises or affect the test results; Not having health conditions in which physical exercise is contraindicated; Achieve a score of no less than 24 on the Mini Mental State Exam; Achieve a score of up to 9.11 on the Baecke Physical Activity Questionnaire.

Exclusion criteria: Miss more than 20% of training sessions; Miss more than three workouts in a row; Failure to attend any of the evaluations will be excluded from the study.

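### Affectivity with the intervention is first rated at week 8, so trainees who leave or are excluded earlier have no score and the intention-to-treat analysis has no earlier value to use

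*Combined protocol and SAP*

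**What the plan says.** All references are to the combined protocol and SAP.

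- **Objectives** lists affectivity with the intervention among 14 specific objectives on which the programmes are to be compared.
- **Outcome measures** describes the instrument, "which consists of answering a quantified scale from +5 to -5", and its referent: "The participant will be instructed to respond to the scale with reference to their feelings throughout the training session and dance class".
- **Experimental design** lists no affect rating at visits one to four, and randomisation follows those visits. At the fifth visit, after 8 weeks, "the physical tests will be reassessed, as well as the application of the questionnaire on affectivity with the intervention" takes place. The only later occasion is the final one: "At the end of the 12 weeks of training, participants will be reassessed on all tests".
- **Arms and Interventions** sets two sessions a week for 12 weeks. Controls keep their usual routine, so they have no session to rate.
- **Eligibility criteria** excludes participants who miss more than 20% of sessions, those who fail to attend an evaluation, and those who "Miss more than three workouts in a row".
- **Sample size** adds three people to each group of nine to cover possible losses, without giving their reasons or timing.
- **Statistical treatment** says non-completers will be analysed by intention to treat, and gives no method for missing values. The training effect is tested by a time-by-group ANOVA.

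**The concern.** How people feel about a programme is an obvious reason for leaving it. When such an outcome is recorded only two thirds of the way through, those most likely to have scored low may already be gone. The observed mean then describes people who were content enough to stay.

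For most other outcomes a leaver at least has a baseline value. Affect towards the training cannot have one, so an early leaver contributes nothing at all, and intention to treat cannot be honoured from observed data.

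What is at stake is the comparison of the two trained arms on this objective. If one programme loses more people because they dislike it, its remaining ratings are raised more than the other's. A real difference could be reduced, or a false one created.

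**Working it through.** **1. How much training precedes the first rating** (Arms and Interventions; Experimental design)

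- Planned sessions: 2 × 12 = 24.
- Sessions by the end of week 8: 2 × 8 = 16, which is 16/24 = 67% of the programme.

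**2. How early a participant can be removed** (Eligibility criteria)

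- More than three misses in a row means four misses: 4 / 2 per week = 2 weeks.
- More than 20% of 24: 0.20 × 24 = 4.8, so five misses. At two sessions a week these can accumulate in 5 / 2 = 2.5 weeks, that is, by week 3.

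Both rules can therefore act five to six weeks before the first rating.

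**3. How many losses the plan allows for** (Sample size)

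- 9 × 3 = 27 and (9 + 3) × 3 = 36, which reproduces the plan's totals.
- Allowance per group: 3/12 = 25%. How many of these losses would come before week 8, or would be due to dislike, is not stated.

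**4. What selection could do to one arm's mean.** The documents give no mean, SD or dropout pattern for affect, so every score here is an assumption.

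*Fixed-score illustration.* Of 12 people, nine would rate +3 and three would rate 0.

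- Full-arm mean: (9 × 3 + 3 × 0)/12 = 2.25.
- Mean if all three low raters leave: 27/9 = 3.00, an error of 0.75.
- Mean if one leaves: 27/11 = 2.45, an error of 0.20.

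*Normal-score simulation.* There are 12 per arm, with an assumed SD of 1.5 to 2 points, and the lowest raters leave before week 8.

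| Lowest raters lost | Overstatement of that arm's mean (points) |
|---|---|
| 1 of 12 | 0.22 to 0.30 |
| 2 of 12 | 0.41 to 0.55 |
| 3 of 12 | 0.59 to 0.79 |

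**5. What that does to the contrast.** The error in the difference between arms is the error in one mean minus the error in the other. Take both arms to have the fixed-score distribution, so that the true difference is zero:

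- Three low raters lost in one arm, none in the other: 3.00 − 2.25 = 0.75.
- Three lost in one arm, one in the other: 3.00 − 2.45 = 0.55.
- Three lost in each arm: 3.00 − 3.00 = 0.

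The bias depends on the imbalance in dislike-driven loss. Losses unrelated to affect add no bias on average.

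**The case against.** **The documents do not say that leavers differ between arms.** This stands. The allowance for losses carries no reason and no timing. The 0.75-point figure is an error in one arm's mean, and it becomes an error in the contrast only if the other arm loses no low raters. The direction is unknown too.

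**Leavers might be brought back at week 8 under intention to treat.** Nothing in the plan describes this, and the attendance rules point the other way. Such a person would also be rating sessions last attended weeks before.

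**Affect is a minor outcome.** It is one of 14 specific objectives, and the sample size rests on the Timed Up & Go. The point limits what can be said about affect and does not touch the main calculation.

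A reader might also infer two stronger criticisms, which the documents do not support:

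- *The shared strength block dilutes the dance-versus-walking contrast.* The dance arm's session "will consist of the same strength training as the traditional concurrent training group", so a whole-session mark does include a common part. But the objective concerns the whole intervention, and a whole-session mark matches it. The outcome text does not say how many marks are taken, and no duration is given for the strength block, so no degree of dilution can be calculated. Making a mark taken after the dance or walking block the outcome would change the question.
- *Two rating occasions cannot cover the dance programme.* The plan says "Classes will be held in four different dance modalities, divided into four modules", but no objective is specific to a module, and module lengths and order are not given.

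**Conclusion.** The concern holds for the timing of the rating. As written, the plan collects no affect mark in the first 16 of 24 sessions, although its own attendance rules can remove a participant by week 2 or 3. No other section supplies an earlier value. The reported outcome will describe stayers, and intention to treat cannot be met for early leavers.

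The size of any bias cannot be derived from the documents. Under the assumed scores above, one arm's mean is overstated by about 0.2 to 0.8 points on the +5 to −5 scale when one to three low raters of 12 are lost. The effect on the contrast runs from zero, when similar losses occur in both arms, up to those same values when only one arm loses low raters. A reader might infer that the comparison will be reversed or hidden. That is possible, but nothing in the plan shows it.

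This is a cheap improvement to a secondary objective. Early ratings cannot be recovered once training is under way.

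**What to change.** **Experimental design and Outcome measures.** Have each trained participant complete the same one-item whole-session scale at the end of one fixed session early in training (for example in week 1 or 2) and at one mid-point before week 8, as well as at weeks 8 and 12. A mark in week 2 comes after at most 4 of 24 sessions instead of 16. State the number of marks and that each is taken at the end of the session.

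**Statistical treatment.** For this outcome, compare the two trained arms on each person's mean of available marks, or with a mixed model using all marks. Include every randomised trainee with at least one mark, even if later excluded for attendance. This needs its own sentence, because a repeated-measures ANOVA conventionally uses only people with complete data and would drop the leavers again. Report by arm how many people gave each mark.

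**Optional.** Separate marks after the strength block and after the walking or dance block may be added as a secondary description. They should not replace the whole-session outcome.

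**Cost.** Two extra one-item marks per trained participant, at sessions already attended, plus data entry and short edits to three sections. No extra visit is needed and the sample size does not change. Two limits remain: anyone who leaves before the first mark is still missed, and a mean of available marks rests on early sessions for leavers but on the whole programme for stayers.

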## **ETHICAL CONSIDERATIONS**

The present work was submitted to the Ethics Committee for Research with Human Beings of the Local University (CAAE: 5570222.0.0000.5347). It is noteworthy that the study will offer a greater than minimal risk to participants in compliance with Resolution N°466 of December 12, 2012 of the National Health Council. Finally, all study participants will sign the Free and Informed Consent Form (Annex 2) having the autonomy to withdraw their participation at any time. Confidential research data will be kept in a safe place, at the Exercise Research Laboratory, which the researcher is part of, for a period of 5 years.

### **Risks and benefits**

The study presents a greater than minimal risk. During the performance of the evaluations and/or training, the participant may feel discomfort or late muscle pain and tiredness due to the intensity of the training. In addition, there is the possibility of some muscle injury occurring during assessments or training. As a way to minimize this risk, all participants will be familiarized with the exercises, will warm up beforehand, have a place to rest and water available throughout their participation and will be accompanied by qualified researchers. During the application of the questionnaires, there may be some embarrassment, since they will be carried out in the form of an interview. To minimize this risk, these assessments will be carried out in a private location. In addition, blood collections may cause small skin lesions,

however, it will be performed by a trained professional seeking to minimize this factor. All procedures may cause physical and mental fatigue due to the large number of questionnaires and evaluations performed. In this sense, to minimize this risk in any of the procedures, the elderly will be questioned periodically during the evaluations about their physical and mental state and if they report any symptoms of discomfort, a break will be held whenever necessary in an appropriate place. If any event occurs during the performance of the procedures, the responsible researcher will be responsible for any and all assistance deemed necessary, with the latter presenting a commitment to provide assistance for any material and immaterial damages resulting from participation in the research. Any type of major damage foreseen or not, resulting from participation in the study, in addition to the right to immediate, full and free assistance, participants will be entitled to compensation, according to items III.2.0, IV.4.c, V.3, V .5 and V.6 of the National Health Council Resolution 466/12.

As a benefit, participants will have feedback on their pre and post intervention results through an individual report. These data can be used to support future physical training, in addition to serving as an indicator of health status. In addition, the participants will benefit from the physiological adaptations provided by the training of the groups with interventions, as well as the gain in relation to functional valences such as gait speed, balance, muscle strength and cardiorespiratory fitness. In order to provide the same gains to participants in the control group, after the 12-week period, they will have the opportunity to carry out one of the proposed interventions according to their preference.

